3.1 Study Type and Design

This is an experimental study employing a prospective randomized controlled trial.

The primary outcome would be to compare the patency of arteriovenous fistula at one, three and six months.

Secondary outcomes shall include:

- To capture data regarding variables that may affect patency of arteriovenous access flow dysfunction post ultrasound-guided fistuloplasty versus fluoroscopy-guided fistuloplasty,
- To compare technical success (defined as clinical palpable thrill, radiographic finding of less than 30% recoil and ultrasonographic finding of continuous segment of dilated vein to 5-6mm and continuous flow rate of more than 500ml/min) in patients with arteriovenous access flow dysfunction receiving ultrasound-guided fistuloplasty versus fluoroscopy-guided fistuloplasty and
- To compare complication rates in patients with arteriovenous access flow dysfunction receiving ultrasound-guided fistuloplasty versus fluoroscopy-guided fistuloplasty

Patients are randomized using simple randomization method. Treatment plans are divided equally between ultrasound-guided fistuloplasty and fluoroscopy-guided fistuloplasty. An application “sealedenvelope.com” is used for this purpose. The application does this via a built in random number generator.

After assessing for eligibility, patients will be randomized equally with a ratio 1:1 to ultrasound-guided fistuloplasty group and fluoroscopy-guided fistuloplasty group.

Both interventions will be done in operation theatre to maintain sterility. After cleaning and draping the area of interest, local anaesthesia is given to the puncture site. A puncture needle is used to gain access to the arteriovenous fistula followed by a guide wire. Then, a sheath with an appropriate size is placed and a balloon catheter of adequate size is inserted over the guide wire and inflated for 2 minutes. Ultrasound is used in the subject group to monitor technical success. On table visualization of continuous segment of dilated vein to 5-6mm and continuous flow rate of more than 500ml/min signifies the end points of the procedure.

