Fluoroscopy is used in the control group to assess for technical success. On table fistulogram visualization of less than 30% recoil of the target lesion signifies technical success. After a satisfactory result, a figure of 8 suture is placed with manual inflow occlusion. Post procedure, patients will be observed for any signs of haematoma or bleeding. If there are no immediate complications, patients will be discharged on the same day.

These procedures will be performed either by vascular surgeons or interventional radiologists below tabled:

OPERATOR	FISTULOPLASTY		CENTRE	DESIGNATION
	ULTRASOUND-GUIDED	FLUOROSCOPY-GUIDED		
[name] [name]	✓		University Malaya Medical Centre	Vascular surgeon
TBD		✓	University Malaya Medical Centre	Interventional radiologist
[name] [name]	✓	✓	Hospital Kuala Lumpur	Vascular surgeon

Cases with serious complications such as extravascular leak or significant pseudoaneurysm will be admitted for monitoring. If the complications are resolved then, the patient will be discharged. Follow-up may be scheduled earlier.

Follow-up will be done at two weeks, one month, three months and six months.

Assessment during follow-up includes:

- Resolution of symptoms (prolonged post dialysis bleeding or difficult access cannulation).
- Reduction of venous dialysis pressure to below predefined threshold values. (the acceptable value is less than 150mmHg)
- Measurement of the volume flow (the acceptable value is more than 500ml/min), flow characteristics (the acceptable characteristic is laminar flow) and diameter of the target lesion (the acceptable diameter is between 5-6mm) using duplex ultrasound.

[figure not shown]
In the event of a negative outcome during the first post fistuloplasty follow-up, it will be determined whether it is due to:

- a missed stenotic segment invisible to ultrasound or
- it is a case of severe stenotic segment refractory to fistuloplasty.

Patients belonging to the former category will cross-over to the fluoroscopic-guided fistuloplasty group. In the latter case, there is no reason to repeat the fistuloplasty regardless of the imaging method (ultrasound or fluoroscopy). Ideally, these particular patients should receive drug-coated balloon (DCB) fistuloplasty which is beyond the scope of this study. There is no alternative apart from switching to fluoroscopic-guided fistuloplasty.

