3.3 Inclusion Criteria

NO.	INCLUSION CRITERIA	EVALUATION METHOD.
1	Patient able to comprehend English or Malay language.	Speak to patient.
2	Patient aged ≥ 18 years and ≤ 80 years.	Examine patient personal data.
3	Patient is willing to comply with protocol.	Ask the patient.
4	Native AVF that is able to provide prescribed dialysis consistently with 2 needles for $>2/3$ of dialysis sessions within 4 consecutive weeks.	Ask the patient & examine dialysis record.
5	Patient has a reasonable expectation of remaining on haemodialysis for 6 months.	Ask the patient.

6	Dampened thrill or pulsatile flow.	Palpate the arteriovenous fistula.
7	Volume flow (VF) <500 ml/min.	Ultrasound doppler measurement.
8	Severe stenosis (>50%) of arteriovenous (AV) access measured on color image and confirmed by peak systolic velocity (PSV) ratio of ≥ 3 in the inflow artery, anastomosis, or in the outflow vein.	Ultrasound doppler measurement.

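### Section 3.1 lets recoil alone score technical success in the fluoroscopy arm; recoil is undefined and ignores the reference vessel, so a still-stenosed lesion can count as a success unless the full definition applies to both arms

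*Combined protocol and SAP*

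**What the plan says.** Section 3.1 of the combined protocol and SAP speaks to technical success in three places.

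- **Secondary outcome.** It is "defined as clinical palpable thrill, radiographic finding of less than 30% recoil and ultrasonographic finding of continuous segment of dilated vein to 5-6mm", followed by a flow requirement above 500 ml/min. The parts are joined by 'and'. The text does not say whether all of them apply to every patient or whether each imaging part belongs to its own arm.
- **Ultrasound arm, procedure text.** The sentence reads, with its last word omitted: "On table visualization of continuous segment of dilated vein to 5-6mm and continuous flow rate of more than 500ml/min signifies the end points of the". This is an absolute lumen and flow standard.
- **Fluoroscopy arm, procedure text.** "Fluoroscopy is used in the control group to assess for technical success", and then: "On table fistulogram visualization of less than 30% recoil of the target lesion signifies technical success". No lumen, flow or residual-stenosis condition is attached.

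Recoil is given no formula or denominator anywhere, and residual stenosis is not mentioned. The balloon is described only as being of adequate size; there is no sizing rule and no requirement of full expansion. Patients enter on a stenosis criterion (section 3.3, criterion 8): "Severe stenosis (>50%) of arteriovenous (AV) access measured on color image".

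**The concern.** Patients are enrolled because the vessel is narrowed relative to its normal calibre. Recoil answers another question: how much of the lumen gained under the balloon is lost on deflation. Without a reference-vessel term, a low recoil figure does not show that the narrowing has gone. The two measures agree when the balloon matches the reference vessel and opens fully, and they separate when it does not.

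Technical success is compared between arms (specific objective 3, and the secondary outcomes in section 3.1). If the control arm is scored on recoil alone while the ultrasound arm must reach an absolute lumen and flow, some control lesions that remain narrowed can be counted as successes, and the two rates are not measured on the same scale.

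**Working it through.** **The plan's own comparison.** Appendix 2 cites one study with both modalities: ultrasound 51/53 = 96.2%, conventional 84/90 = 93.3%. The gap is 2.9 points, with 6/90 conventional failures. The plan's sample size (22 per group, 27 with dropout) does not enter this point.

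**Definitions assumed, since the plan gives none.** D = balloon diameter, M = lumen after deflation, R = reference diameter.

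- Recoil = (D - M)/D
- Residual stenosis = (R - M)/R

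**What the 30% rule guarantees.** Recoil below 30% means M > 0.7 x D, so residual stenosis is below 1 - 0.7 x (D/R).

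| D/R | Upper bound on residual stenosis |
|---|---|
| 1.0 | 30% |
| 0.9 | 37% |
| 0.8 | 44% |
| 0.71 | about 50% |
| 0.6 | 58% |

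Below a ratio of about 0.71, a lesion can pass the recoil rule while still above the plan's own 50% entry limit.

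**Illustrations, with an assumed 6 mm reference vein.**

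| Case | Lumen after | Recoil | Residual stenosis |
|---|---|---|---|
| 6 mm balloon, fully opened | 4.26 mm | 29% | 29% |
| 4 mm balloon, fully opened | 3.0 mm | 25% | 50% |
| 3.5 mm balloon, fully opened | 2.8 mm | 20% | 53% |
| 6 mm balloon, waist stays at 3 mm | 2.8 mm | 7% against the lumen reached; 53% against the nominal balloon | 53% |

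The small-balloon cases pass the recoil rule on either denominator. The non-yielding lesion passes only if recoil is taken against the lumen reached at inflation; against nominal balloon size it fails.

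**The same cases under the full secondary-outcome definition.** If the duplex part is required in both arms, all four fail the 5-6 mm criterion. That includes the first, which both percentage measures would pass. Which text governs therefore changes the score.

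**Scale in this trial.** Expected control failures: 27 x 6/90 = 1.8. One patient in 27 is 1/27 = 3.7 points, more than the 2.9-point gap.

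**Direction.** Suppose a share f of the cited failures would be rescored as successes. The value of f is an assumption, because Appendix 2 gives no causes of failure.

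- Fluoroscopy arm only, difference = 51/53 - (84 + 6f)/90: +1.2 points at f = 0.25, -0.4 at 0.5, -3.8 at 1.
- Both arms equally, difference = (51 + 2f)/53 - (84 + 6f)/90: +2.2 at f = 0.25, +1.4 at 0.5, 0 at 1.

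The sign changes only if the rescoring is confined to the fluoroscopy arm.

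**The case against.** The strongest reply is that the secondary-outcome paragraph is the formal definition, is stated for both groups, and joins its parts with 'and'. Read that way, a lumen of 2.8 or 3.0 mm fails and nothing is misscored. The fluoroscopy sentence could then be only an on-table end point, parallel to the ultrasound one. This reading is open and would remove the problem. It is not secured by the text: the fluoroscopy sentence uses the outcome's own name, and requiring every part in both arms would mean a fistulogram for each ultrasound patient, which sits badly with the avoidance of contrast claimed in sections 3.10 and 3.11.

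The thrill requirement remains even on an arm-specific reading. It is a weak safeguard: it carries no grade, and patients can enter with a dampened thrill (section 3.3, criterion 6) alongside a stenosis above 50%.

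The small-balloon cases assume undersizing, whereas the plan asks for an adequate size. That is fair. They show what the rule permits, not how often it would happen. Recoil may also be loose usage for residual narrowing, in which case the fix simply states the intent.

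A reader might infer that lesions which never opened are routinely scored as successes. The documents do not support this. It depends on an unstated denominator, and the mention that "it is a case of severe stenotic segment refractory to fistuloplasty" concerns a negative result at the first follow-up, not a balloon waist on the table, and gives no frequency.

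Duplex diameter and flow are measured in both arms from two weeks, so a lesion that stays narrow would be seen. Those readings belong to follow-up, however, and do not correct the technical-success score.

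**Conclusion.** The point stands in conditional form. Section 3.1 gives two statements of technical success that can score the same control patient differently, and the one specific to fluoroscopy rests on an undefined recoil percentage with no reference vessel. Applied as written, and with recoil taken against the balloon, it admits residual stenosis up to 1 - 0.7 x (balloon/reference diameter). If all parts of the formal definition are required in both arms, these lesions are caught.

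The effect is confined to a secondary outcome; patency and the sample size are untouched. With about 1.8 failures expected in 27 control patients, if the cited 6/90 rate carries over, a single misscored patient moves the rate by more than the cited gap between modalities.

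A reader might go further and conclude that the rule would reverse the comparison. That is not established: it needs an assumed share of rescored failures and rescoring in one arm only.

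**What to change.** For scoring the outcome only, make two changes in section 3.1.

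1. Define the radiographic component as residual diameter stenosis of the target lesion below 30%, relative to the adjacent reference lumen on the completion fistulogram. Recoil can stay as a descriptive item, with its denominator stated.
2. Reconcile the secondary-outcome definition with the procedure text, stating which components score technical success in each arm.

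The on-table procedural end point is left to the investigators; nothing here changes how the procedure is carried out. The first change costs one sentence and uses the fistulogram already taken, with no extra imaging. The second is a matter of wording, unless the sponsor chooses to require both imaging parts in both arms. The downside is that the fluoroscopy technical-success rate may be slightly lower.

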Study Population	All adult patients with arteriovenous access flow dysfunction in Hospital Kuala Lumpur and University Malaya Medical Centre during the period 1 July 2023 – 30 June 2024.
Study Design	A randomized controlled study. Selected subjects will be randomized into ultrasound-guided fistuloplasty and fluoroscopy-guided fistuloplasty groups in a ratio of 1:1
General Objective	To investigate patencies in patients with arteriovenous access flow dysfunction receiving ultrasound-guided fistuloplasty versus fluoroscopy-guided fistuloplasty at 6 months
Specific Objectives	
 To investigate patencies in patients with arteriovenous access flow dysfunction receiving ultrasound-guided fistuloplasty versus fluoroscopy-guided fistuloplasty at 6 months, To capture data regarding variables that may affect patency of arteriovenous access flow dysfunction post ultrasound-guided fistuloplasty versus fluoroscopy-guided fistuloplasty, To compare technical success in patients with arteriovenous access flow dysfunction receiving ultrasound-guided fistuloplasty versus fluoroscopy-guided fistuloplasty, and To compare complication rates in patients with arteriovenous access flow dysfunction receiving ultrasound-guided fistuloplasty versus fluoroscopy-guided fistuloplasty.
Study endpoints/outcomes	(a) Patency of arteriovenous fistula over a period of six months post fistuloplasty; (b) Resolution of symptoms; (c) Technical success; (d) Percentage increase in volume flow.
Sample Size	54 subjects.
Study Duration	1 July 2023 - 31 December 2024.

1. Background and Significance

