3.8 Study Visits and Procedures

Follow-up will be done at two weeks, one month, three months and six months.

Assessment during follow-up includes:

- Resolution of symptoms (prolonged post dialysis bleeding or difficult access cannulation).
- Reduction of venous dialysis pressure to below predefined threshold values. (the acceptable value is less than 150mmHg)
- Measurement of the volume flow (the acceptable value is more than 500ml/min), flow characteristics (the acceptable characteristic is laminar flow) and diameter of the target lesion (the acceptable diameter is between 5-6mm) using duplex ultrasound.

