3.11 Risk Benefit Assessment

As stated above, there is minimal risk from the investigational study procedures. Study findings shall avoid radiation hazard and eliminates contrast-related hazards in already renal compromised patient. The expected benefit outweighs the minimal risk to subjects and thus this study should be supported. If any injuries do occur as a direct result of participating in the study, treatment for such injuries shall be provided.

Leskovar et al.³ reported 93% technical success with minor complications that were self-limiting and can be managed successfully by direct pressure. Complications include:

1. venous rupture (3.5%),
2. post-procedural thrombosis (1%),
3. balloon rupture with conversion to surgical procedure (0.5%),
4. guide wire false route (0.5%), and
5. pseudo-aneurysm at puncture site (0.5%).

Given that the intervention procedure is the exact same technique, as long as a minimum image quality is available, the outcome would essentially be the same for either imaging techniques. Complications arising from image quality would no longer matter.

In the case of **venous rupture**: tiny venous rupture of pseudoaneurysm can be managed by direct hand compression for 20 minutes and balloon occlusion or by placing covered stent. Extravascular leak or significant pseudoyaneurysm require emergency surgical repair.

Cases of **acute thrombotic occlusion** at access and plasty site can be managed successfully by giving additional heparin, thromboaspiration and over-the-wire Fogarty catheter.

Difficulty in recovering **ruptured balloon** requires either surgical removal or using ultrasound-guided snare.

We provide a comparison between the two visual modalities of fistuloplasty, as reported by Cho et al.⁴ in the table below.

NO.	COMPLICATIONS	FISTULOPLASTY		MITIGATION
		ULTRASOUND-GUIDED	FLUOROSCOPY GUIDED	
1	Vessel rupture	2/53 (3.8%)	1/90 (2.2%)	Successfully managed by balloon tamponade technique
2	Access thrombosis	1/53 (1.9%)	1/90 (2.2%)	-
3	Aneurysm development	-	1/90 (2.2%)	-
4	Sheath haematoma	-	1/90 (2.2%)	-

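### Complication rates are a compared outcome, but no follow-up visit lists complications, so later events may go unrecorded or be counted only as patency loss

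*Combined protocol and SAP*

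**What the plan says.** Section 3.1 lists among the secondary outcomes: "To compare complication rates in patients with arteriovenous access flow dysfunction receiving ultrasound-guided fistuloplasty versus fluoroscopy-guided fistuloplasty". The same aim is specific objective 4 in the synopsis. The synopsis endpoint list, however, has only patency, symptom resolution, technical success and change in volume flow.

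On ascertainment, section 3.1 states: "Post procedure, patients will be observed for any signs of haematoma or bleeding". It continues: "If there are no immediate complications, patients will be discharged on the same day". For recognised serious events it adds: "Cases with serious complications such as extravascular leak or significant pseudoaneurysm will be admitted for monitoring". It also allows follow-up to be brought forward.

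Visits are at two weeks and at one, three and six months. The assessment lists in sections 3.1 and 3.8 cover access symptoms, venous dialysis pressure, and duplex volume flow, flow character and target-lesion diameter. Complications are not listed. For a poor result at the first visit, section 3.1 offers two explanations: a stenosis that ultrasound missed, or a stenosis that resists dilatation.

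Section 3.11 names the complications to be expected. They include thrombosis, pseudoaneurysm at the puncture site and aneurysm development. Section 3.9 assigns the secondary objective to logistic regression without defining a complication event.

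**The concern.** An outcome compared between arms needs a definition, a window and a planned point of collection. Here the only planned collection is on the day of the procedure and is limited to haematoma and bleeding. A patient who is well at discharge and later develops a thrombosis or a puncture-site pseudoaneurysm has no stated route into the complication count.

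Thrombosis is the clearest case. Duplex at the next visit would show lost flow, but the plan would record this as failed patency, and the two-way classification at the first visit has no category for it.

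Events not collected at visits cannot be recovered at analysis. The trial could then report a rate made up largely of events noticed on the day under the label of an overall complication rate. Sections 3.10 and 3.11 justify the trial partly on safety, so this figure will be read.

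**Working it through.** **Plan's own figure.** Section 3.6 gives no figure for complications; its sample size rests on response rates of 90% and 52.4%. With pooled variance, two-sided alpha 0.05 (sidedness assumed) and 80% power:

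- mean proportion = (0.90 + 0.524)/2 = 0.712; difference = 0.376
- n = [1.96 × √(2 × 0.712 × 0.288) + 0.842 × √(0.90 × 0.10 + 0.524 × 0.476)]² / 0.376² = 21.6, rounded up to 22
- 22 × 1.2 = 26.4, rounded up to 27 per arm

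Both printed figures reproduce. Neither concerns complications.

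**Inputs for complications.** These are the counts in the section 3.11 table from the cited comparison of the two guidance methods. I assume one complication per patient.

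| Event | Ultrasound | Fluoroscopy |
|---|---|---|
| Vessel rupture | 2/53 | 1/90 |
| Access thrombosis | 1/53 | 1/90 |
| Aneurysm | none | 1/90 |
| Sheath haematoma | none | 1/90 |
| All | 3/53 = 5.7% | 4/90 = 4.4% |

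**Expected events with 27 per arm.**

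- All captured: 27 × 3/53 = 1.5 and 27 × 4/90 = 1.2; total 2.7.
- Thrombosis and aneurysm not counted: 27 × 2/53 = 1.0 and 27 × 2/90 = 0.6; total 1.6.
- Events at risk of being lost: 2.7 − 1.6 = 1.1, if all thromboses and aneurysms arise after discharge and none is recorded. Section 3.11 gives no timing, so the range is 0 to 1.1.

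**Can the contrast be tested?** With 27 per arm, Fisher's exact test needs at least 6 events against 0 for P < 0.05. Its power, by enumeration at the rates above, is 0.13% with full capture and 0.02% with the reduced count.

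**Does incomplete capture push the contrast one way?** Ultrasound-to-fluoroscopy ratio by scenario:

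| Events not counted | Rates | Ratio |
|---|---|---|
| None | 3/53 vs 4/90 | 1.27 |
| Thrombosis only | 2/53 vs 3/90 | 1.13 |
| Aneurysm only | 3/53 vs 3/90 | 1.70 |
| Thrombosis and aneurysm | 2/53 vs 2/90 | 1.70 |

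The ratio can move either way. The source table is also inconsistent: it prints each 1/90 as 2.2%, whereas 1/90 = 1.1% and 2/90 = 2.2%. If the percentages are right and the counts wrong, full capture is 3/53 vs 8/90, ratio 0.64. Rupture plus haematoma alone is then 2/53 vs 4/90, ratio 0.85. On that reading the starting direction reverses, and the expected total with 27 per arm becomes 1.5 + 27 × 8/90 = 3.9.

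**The case against.** The strongest reply is that surveillance does not stop at discharge. Serious cases are admitted, follow-up may be earlier, and every patient has duplex at four visits. A thrombosed access would show as lost flow, and prolonged bleeding after dialysis is asked about each time. The visit list is introduced as what assessment includes, so it may not be exhaustive; a figure next to it is not shown, and the data collection form mentioned in section 3.14 is not among the documents. All of this stands. It rules out the inference that complications are sought only on the day, or that thrombosis and pseudoaneurysm are necessarily missed.

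It does not close the gap. Admission and earlier review follow once a complication has been recognised; they are not a systematic check of patients who left well. Duplex diameter is specified for the target lesion, whereas the pseudoaneurysm in section 3.11 is at the puncture site. Lost flow has no stated path to being counted as a complication.

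A second reply is that visits are the same in both arms, so under-recording need not be differential, and that so few events make the contrast uninformative even with full capture. Both parts are fair. At University Malaya Medical Centre different operators perform the two procedures, so recording without a shared definition could follow arm, but that is a possibility and not a finding. With about three events expected, one unrecorded event still changes the reported rate materially.

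**Conclusion.** The point holds as a gap in ascertainment. Objective 4 compares complication rates, yet the documents give complications no definition, window or place at any visit. Followed as written, the plan may leave later events unrecorded or count them only as patency loss, and the reported rate would be incomplete. On the section 3.11 counts, and assuming those rates apply here, this concerns between 0 and about 1.1 of 2.7 expected events.

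A reader might infer that the between-arm safety comparison will be biased, perhaps against ultrasound. The documents do not support this. The illustration rests on seven events from a non-randomised study, event timing is not given, the ratio moves in both directions across scenarios, and the printed counts and percentages disagree. Treating the sheath haematoma as a lost event would not be reasonable either, since haematoma is one of the two things staff are told to look for. A reader might also assume that thrombosis and pseudoaneurysm typically appear after discharge. Section 3.11 does not say so, and its account of acute thrombotic occlusion could equally describe events around the procedure.

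With so few events expected, the complication comparison is descriptive whatever is done. The case for change is completeness of the record, not power.

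**What to change.** - In section 3.8, and in the matching list in section 3.1, add a fixed complication checklist to every scheduled visit in both arms: haematoma, bleeding, thrombosis, pseudoaneurysm or aneurysm, infection, and readmission or surgery on the access. Use the examination and duplex already done there.
- Add complications from procedure to six months to the synopsis endpoints.
- State that a thrombosis counts as a complication as well as a loss of patency.
- Report complications by randomised arm, flagging those that occur after cross-over to fluoroscopy. Section 3.1 provides for that cross-over and section 3.9 specifies a per-protocol analysis, but neither says which arm such an event belongs to.
- Present the comparison as descriptive counts and proportions.

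The cost is a few more lines on the data collection form and some protocol wording. No new visit or scan is needed, and clinical management does not change. The downside is that observed complication rates will be higher than under same-day recording.

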3.6 Sample Size

Based on a power of 80% ($\beta=0.2$), alpha of 0.05, a response anticipated difference of 90% in ultrasound-guided fistuloplasty group and 52.4% in fluoroscopy-guided fistuloplasty group, the calculated sample size for each group is 22 patients. Allowing for 20% dropout, a final sample size of 27 per group will be used.

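### No masked or independent reading of the follow-up duplex is described, patency is undefined, and the cause-of-failure step needs knowledge of the arm; at 22 per group, two reclassified patients can change the result

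*Combined protocol and SAP*

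**What the plan says.** The primary outcome in 3.1 is patency at one, three and six months. No section states what makes a fistula patent.

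Sections 3.1 and 3.8 list the same follow-up assessments: symptoms, venous dialysis pressure, and a duplex scan giving flow, flow character and lesion diameter. The flow item reads "Measurement of the volume flow (the acceptable value is more than 500ml/min". No rule combines these measures into a verdict of patent or not patent. The person who scans is not named, and no measurement method or repeat reading is set. The available text has no statement on masking of patients, operators or assessors.

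Section 3.1 then adds a step: "In the event of a negative outcome during the first post fistuloplasty follow-up, it will be determined whether it is due to" a narrowed segment that ultrasound did not show, or a severe stenosis that does not yield to the balloon. Patients in the first category cross over to the fluoroscopy group. Section 3.9 analyses the data per protocol and does not say how crossed-over patients are counted.

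Section 3.6 assumes "a response anticipated difference of 90% in ultrasound-guided fistuloplasty group and 52.4% in fluoroscopy-guided fistuloplasty group", from which "the calculated sample size for each group is 22 patients", and then: "Allowing for 20% dropout, a final sample size of 27 per group will be used".

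**The concern.** Operators cannot be masked to the guidance method, so the protection has to come from how follow-up is read. Here the reading is open in three ways.

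- **Who reads.** Nothing prevents the operator from scanning their own patient. The operator table in 3.1 shows one ultrasound-guided operator at each centre.
- **What counts.** With patency undefined, an assessor who knows the arm has discretion over which measures decide the outcome as well as over the reading itself.
- **What follows.** The cause-of-failure judgement depends on the arm, can trigger cross-over, and may then affect who remains in the per-protocol set. One arm-aware call can therefore touch both the outcome and the analysis population.

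The on-table targets also differ. The ultrasound arm is treated to a flow and diameter target that reappears at follow-up, whereas the fluoroscopy arm is treated to a limit on recoil. An ultrasound operator who rescans would be marking their own end point.

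**Working it through.** **Step 1. Reproduce the sample size.** Inputs from 3.6: p1 = 0.90, p2 = 0.524, alpha 0.05, power 80%. From 3.1: 1:1 allocation. Sidedness is not stated; I assume two-sided, with no continuity correction.

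n = [z(0.975)·√(2·p̄·(1−p̄)) + z(0.80)·√(p1(1−p1) + p2(1−p2))]² / (p1−p2)²

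- p̄ = (0.90 + 0.524)/2 = 0.712
- First term: 1.960 × √(2 × 0.712 × 0.288) = 1.255
- Second term: 0.842 × √(0.0900 + 0.2494) = 0.490
- n = (1.255 + 0.490)² / 0.376² = 21.6, so 22 per group, as stated.

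For dropout, 22 × 1.2 = 26.4 gives the stated 27; 22/0.8 = 27.5 would give 28. The difference does not matter here.

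**Step 2. How many reclassified patients change the answer?** Expected counts at 22 per group are 0.90 × 22 = 19.8 and 0.524 × 22 = 11.5, so 20 and 12 are close to plan. I use the uncorrected chi-square test for two proportions, because the sample size is built on proportions (3.9 names a t-test).

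| Ultrasound | Fluoroscopy | z | Chi-square p | Fisher p |
|---|---|---|---|---|
| 20/22 | 12/22 | 2.71 | 0.007 | 0.016 |
| 19/22 | 12/22 | 2.31 | 0.021 | 0.045 |
| 18/22 | 12/22 | 1.94 | 0.052 | 0.104 |

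First row: pooled proportion 32/44 = 0.727; SE = √(0.727 × 0.273 × 2/22) = 0.134; z = (8/22)/0.134 = 2.71.

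Third row: pooled proportion 30/44 = 0.682; SE = 0.140; z = (6/22)/0.140 = 1.94.

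Two moves cross 0.05. The count depends on the starting point. From 20/22 versus 11/22, three moves are needed by chi-square (p = 0.060) and two by Fisher (p = 0.055). If all 27 per group are analysed, starting from 24/27 versus 14/27 (p = 0.003), four moves are needed by chi-square (20/27, p = 0.091) and three by Fisher (21/27, p = 0.086).

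**Step 3. False-positive rate under an assumed reading shift.** Assume no true difference, 22 per group, and true patency between 52.4% (3.6) and 77.6% (the six-month figure of one series in Appendix 1) in both arms. Rejection rates come from exact binomial enumeration of the two-sided pooled z-test.

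| Assumed rise in apparent patency, one arm only | Rejection rate |
|---|---|
| none | about 5% |
| 5 points | 6–7% |
| 10 points (about 2 of 22) | 10–14% |
| 15 points | 17–29% |

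The shifts are assumptions. The documents give neither duplex measurement error nor a distribution of follow-up flow.

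**Step 4. The cross-over route.** As an illustration, suppose the ultrasound arm truly has 18/22 patent (81.8%), and two of its four failures are judged to be missed stenoses, cross over, and are dropped from the per-protocol set. The arm then reads 18/20 = 90.0%. Against 12/22, the pooled proportion is 30/42 = 0.714, SE = √(0.714 × 0.286 × (1/20 + 1/22)) = 0.140, and z = (0.900 − 0.545)/0.140 = 2.54, p = 0.011 instead of 0.052. Whether such patients would be dropped is not stated.

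**The case against.** **Patency is not shown to rest on duplex flow.** This stands. Flow above 500 ml/min is one of several follow-up values; the synopsis lists percentage increase in flow as an endpoint separate from patency; and the same flow value belongs to technical success, a secondary outcome. The missing definition is the prior defect. It widens the room for judgement.

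**Absence of masking is inferred from silence.** Partly stands. The front page and the flowchart were not available to me. The sections where masking would be put into practice are silent, however, and the cause-of-failure step cannot be carried out without the allocation.

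**The shared cut-off.** A reader might infer bias because the entry limit, "Volume flow (VF) <500 ml/min", meets the acceptable follow-up value at the same number. The documents do not support this. The entry limit applies to both arms before randomisation. What would matter is how many follow-up flows lie near 500 ml/min, which is not given. Random measurement error near the limit would not show bias either, since it occurs in both arms whether or not the reader is masked.

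**A tilt towards ultrasound.** A reader might also infer this direction. It is not established: no text says who scans, and at Hospital Kuala Lumpur the listed operator performs both techniques.

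**The planned difference is large.** It is 37.6 points, and a 5-point reading shift barely moves the error rate. That is true. Only shifts of about two patients or more matter materially, and their occurrence cannot be derived from the documents.

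**Conclusion.** The point holds as an unprotected assessment; it is not a demonstrated bias. The plan describes no masked or independent follow-up reading, leaves patency undefined, and includes an arm-dependent judgement that can lead to cross-over and possibly to loss from the per-protocol set.

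Its importance comes from the trial's size. Near the planned result at 22 per group, two reclassified ultrasound patients move chi-square p from 0.007 to 0.052; other starting counts, or 27 per group, need two to four. A one-arm shift of about two patients would raise the false-positive rate from about 5% to 10–14%.

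These figures assume a binary outcome compared by a two-sided test of proportions, and the shifts are hypothetical. The sponsor should act, because arm-aware readings cannot be repaired after collection.

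**What to change.** In 3.8, with matching text in 3.1:

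1. State which follow-up measures make up patency and how they combine.
2. Send the duplex request with the study number only and without the arm. Section 3.14 already uses identification numbers on data sheets.
3. Take flow as the mean of three readings at one fixed site.
4. Record flow, flow character and diameter before allocation is disclosed and before any judgement on cause of failure or cross-over.
5. Where existing staff allow, have the scan done by someone who did not perform that patient's procedure. The documents do not show whether such staff are available, so this item is conditional; items 1 to 4 need no new staff.

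None of this alters a treatment rule or the sample size. The cost is protocol wording, a revised request form, some scheduling effort, and two extra flow readings per scan.
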